## 1.0 BACKGROUND & RATIONALE

### 1.1 BACKGROUND

#### *Clinical Stage III Melanoma*

Clinical stage III melanoma is defined as patients with clinically detected, palpable (macroscopic) lymph nodes with or without in-transit or satellite metastases and no evidence of distant metastases. This group of patients is staged as at least Stage IIB/IIIC (by AJCC version 7) or IIIB/IIIC/IIID (by AJCC version 8) and has heterogeneous outcomes when viewed as a whole with 5-year survival varying from 32-83%.

In a recent analysis of 144 clinical Stage III melanoma patients with a BRAF mutation identified at MD Anderson, average time to disease relapse was less than 2 year, highlighting the high-risk nature of this disease stage (MD Anderson internal data). Traditionally, this group of patients have high-risk disease even with upfront surgery and newly available adjuvant therapy options including high dose ipilimumab, nivolumab, dabrafenib and trametinib and pembrolizumab.

#### *Neoadjuvant Therapy*

Neoadjuvant (preoperative) therapy has a long history of use in a variety of solid tumors including breast cancer, rectal cancer, gastric cancer, esophageal cancer and bladder cancer. The use of neoadjuvant therapy in melanoma was previously limited in use due to limited number of drugs producing benefit and the most commonly used regimen was a multi-drug combination approach known as biochemotherapy. Although this regimen yielded response rates of approximately 40%, patients experienced extensive toxicity and required inpatient administration of this regimen. However, as multiple new targeted and immunotherapy options have been FDA approved in melanoma since 2011 that have improved the survival of metastatic patients, there is great interest in using these agents in earlier stage disease patients.

Neoadjuvant therapy offers a number of potential advantages for patient care. Successful neoadjuvant therapy that results in tumor shrinkage can potentially render surgery less morbid. Earlier administration of systemic therapy can potentially more expeditiously destroy micrometastases which may have the opportunity to grow during the relatively immunosuppressed period after surgery and subsequent recovery. Response to neoadjuvant therapy can be helpful in determining patient prognosis as complete lack of viable tumor in the resected specimen (pathologic complete response or pCR) has been correlated with improved patient outcomes. Additionally, neoadjuvant trials offer the opportunity for biomarker discovery as longitudinal blood and tumor samples can be obtained to facilitate study of mechanisms of treatment response or resistance. Neoadjuvant therapy can be a robust platform for drug development and has been utilized as an avenue for new drug registration.

Prior to 2014, neoadjuvant therapy in melanoma traditionally had been limited to a multidrug regimen called biochemotherapy. This 5-drug regimen consisted of infusional therapy requiring inpatient hospital stays and was associated with significant hematologic toxicity, cardiac and pulmonary toxicities. This regimen did produce 22% partial response by imaging and pathologic complete response rates of approximately 26%. Due to the toxicity and need for inpatient admission, this regimen was not widely used across the melanoma community.

Another neoadjuvant trial utilized ipilimumab 10mg/kg which was given intravenously every 3 weeks for 2 doses prior to surgery. In this trial, there were no pathologic complete responses and only a small number of patients achieving a minor pathologic response. This regimen was thus not widely utilized in the neoadjuvant setting.

## 1.2 MODERN NEOADJUVANT TRIALS

### *Dabrafenib plus trametinib*

There are two mature studies evaluating the combination of dabrafenib (150 mg twice daily) and trametinib (2 mg daily) in the neoadjuvant setting.

In the Combi-Neo trial (MD Anderson Protocol 2014-0409; NCT02231775), patients with stage IIIB/C (AJCC 7th edition) or oligometastatic stage IV *BRAF*-mutant melanoma were randomized to either surgery followed by standard of care adjuvant therapy (which could be observation alone, high dose interferon, pegylated IFN- $\alpha$ 2b, high-dose ipilimumab, or biochemotherapy) or neoadjuvant combination dabrafenib and trametinib (8 weeks) followed by 44 weeks postoperatively. Interim analysis of the initial 21 patients enrolled demonstrated that neoadjuvant dabrafenib and trametinib was associated with a high imaging response rate (77%) and pCR rate of 58%. At a median follow-up of 18.6 months, neoadjuvant targeted therapy was associated with significantly better RFS than patients randomized to surgery followed by possible postoperative adjuvant therapy (HR 60.2, 95% CI 6.7-7965, p<0.0001).

There was also improved distant metastasis-free survival (HR 0.024, p=0.001) and trend towards improved overall survival (HR 0.28, [=0.22) for the neoadjuvant dabrafenib and trametinib treated patients. Of note, pCR patients had a trend towards improved relapse free survival and overall survival compared to the upfront surgery patients and did have statistically significant improvement in distant metastasis-free survival over non-pCR patients; indicating that pathologic responses can influence patient survival outcomes.

This regimen also showed a manageable safety profile for dabrafenib and trametinib, similar to that observed in patients with metastatic melanoma, with pyrexia and chills as the most commonly reported adverse events (AEs), none of which interfered with the ability to carry out planned surgery. There were no progression events during the neoadjuvant treatment and all patients were able to proceed to surgical intervention.

Due to the clear superiority in achieving the primary objective of improved progression free survival in the neoadjuvant dabrafenib and trametinib treated patients, the MD Anderson Data Safety Monitoring Board closed the randomized trial at only a quarter of the planned accrual. Thus, our group re-designed the trial as a single-arm study of neoadjuvant dabrafenib and trametinib. This redesigned trial is now powered to determine patient survival outcomes based on the pathologic response at the time of surgery.

As of September 2019, a total of 37 patients have been treated with neoadjuvant, dabrafenib and trametinib on this protocol at MD Anderson with an overall pCR rate of 40% in the 32 patients who have gone to surgery. As additional patients have been treated, we have been able to ascertain trends in survival and recurrence. Specifically, in the patients who did not achieve a pCR, we have noted 11% of patients have experienced locoregional recurrence and 43% have developed CNS disease. In the patients who did achieve a pCR, locoregional relapse rate was 23% and CNS metastasis development was 8%. These data indicate clearly divergent outcomes in patients depending on pathologic response and demonstrate the need to improve outcomes in those not achieving a pCR (unpublished data). 17.6 months, 38% of patients developed distant extracranial relapse, 38% had loco-regional relapse and 23% intra-cranial relapse, including 35% of pCR patients.

Both of these studies demonstrate that neoadjuvant, dabrafenib and trametinib can achieve high rates of pCR and that pCR patients tend to have superior clinical outcomes compared to the non pCR patients. However, relapses, with tendency for CNS-specific relapse in the non pCR cohort of patients is a concerning finding.

### *Neoadjuvant immune checkpoint inhibitors*

#### Pembrolizumab

NCT02434354 enrolled patients with clinical stage III or resectable stage IV melanoma. Patients received one dose of neoadjuvant pembrolizumab 3 weeks prior to surgery followed by a year of adjuvant pembrolizumab. Interestingly, 8/27 treated patients had pCR or near pCR (<10% viable tumor) at time of surgery. Neoadjuvant pembrolizumab was well tolerated with no major AEs prohibiting on- time surgical procedure. All patients with pCR or near pCR remain free of disease with median follow up time of 25 months; again, highlighting the prognostic importance of pCR^25.

#### Ipilimumab plus nivolumab

NCT02519322 is a phase 2 trial conducted at MD Anderson Cancer Center in which patients with clinically detected but resectable stage III and oligometastatic stage IV melanoma are randomized to receive either nivolumab alone (3 mg/kg every 2 weeks for up to 4 doses, Arm A) or in combination with ipilimumab (nivolumab 1 mg/kg with ipilimumab 3 mg/kg every 3 weeks for up to 3 doses,

Arm B) prior to surgery. Adjuvant nivolumab (3 mg/kg every 2 months) will be administered postoperatively to patients on both arms for 6 months. In this single-institution trial run at MD Anderson Cancer Center, planned accrual was 40 patients, however this trial was closed after 23 patients were enrolled (12 patients to Arm A, 11 to Arm B) due to concerns about poor efficacy in Arm A and toxicity in Arm B. Neoadjuvant nivolumab (Arm A) was associated with pCR in 25% of patients and 25% radiographic response rate. However, 17% of patients receiving neoadjuvant nivolumab therapy were unable to proceed to surgery due to disease progression and development of distant metastases during neoadjuvant treatment. All patients who received neoadjuvant ipilimumab plus nivolumab (Arm B) underwent surgery, with 45% pCR and 73% radiographic response rate. However, patients who received neoadjuvant ipilimumab plus nivolumab also experienced significantly higher numbers of grade 3 treatment-related AEs (73% in Arm B versus 8% in Arm A), which at times led to surgical delays due to the need for high dose steroids to mitigate immune mediated toxicities.

The OpACIN trial randomized 20 patients with resectable, clinical nodal disease to adjuvant or neoadjuvant ipilimumab 3 mg/kg and nivolumab 1 mg/kg either as 4 doses given postoperatively or split as 2 doses given preoperatively and 2 doses postoperatively. Although most patients (18 of 20) were unable to complete all 4 planned doses due to grade 3 or 4 toxicities, neoadjuvant therapy produced 3 pCR and 3 near pCR of the 10 treated patients. Patients with pCR or near pCR had not developed any disease relapse with a median follow up of 25.6 months. In total, 4 patients in the adjuvant arm relapsed while 2 patients in the neoadjuvant arm relapsed with median 32 month follow up.

The OpACIN-Neo study (NCT02977052) is an open-label, three-arm phase II trial in which 86 stage III melanoma patients were randomized 1:1:1 to receive either: (Arm A) 2 courses of ipilimumab 3 mg/kg + nivolumab 1 mg/kg every 3 weeks; n=30; (Arm B) 2 courses of ipilimumab 1 mg/kg + nivolumab 3 mg/kg every 3 weeks, n=30; or (Arm C) 2 courses of ipilimumab 3 mg/kg, directly followed by 2 courses of nivolumab 3 mg/kg every 2 weeks, n=26, with the second dose of ipilimumab and the first dose of nivolumab given on the same day to keep the overall duration of therapy the same as the other two arms. Patients in all three treatment arms then undergo surgery at 6 weeks.

In Arm A, 47% of patients had pCR and 23% had near pCR and this cohort experienced 40% grade 3-4 immune mediated toxicities. In Arm B, 57% of patients had a pCR, 7% near pCR and 20% experienced grade 3-4 toxicities. In Arm C, 23% of patients had pCR, 23% had near pCR and grade 3-4 toxicity rate was 50%. Thus, the authors concluded that the combination therapy groups were most effective in producing pCR/near pCR but that toxicity was less in the group using ipilimumab 1mg/kg with nivolumab 3mg/kg.

***Neoadjuvant checkpoint inhibitor therapy in combination with other therapies***

There are also ongoing phase I and II studies to investigate combining immune checkpoint blockade with targeted therapies for patients with *BRAF* mutated melanoma.

The NeoTrio trial (NCT02858921) is a phase II study of patients with *BRAF* mutant resectable stage IIIB, IIIC and IV melanoma who are randomized to receive either dabrafenib plus trametinib for 2 weeks followed by pembrolizumab for 50 weeks (Arm A), concurrent dabrafenib plus trametinib and pembrolizumab for 52 weeks (Arm B), or pembrolizumab monotherapy for 52 weeks (Arm C). Of the 52 weeks of systemic therapy in each arm, 12 weeks are administered in the neoadjuvant setting and the remaining 40 weeks of therapy are administered in the adjuvant setting. The primary outcome is pathological response rate after 12 weeks of treatment, assessed at the time of surgery. Secondary outcomes include objective response rate by RECIST criteria, RFS, OS, and safety.

The NeoACTIVATE trial (NCT03554083) is enrolling *BRAF* mutated patients with vemurafenib (*BRAF* inhibitor), cobimetinib (MEK inhibitor) with atezolizumab (anti PD-L1 antibody) with clinical stage III melanoma.

Neoadjuvant therapy is being administered for three months prior to surgery and an adjuvant phase with triplet therapy is also offered. The primary objective is pCR rate.

We have previously demonstrated that patients who do not achieve a pCR tend to have a more exhausted T cell phenotype in their baseline, on-treatment and surgical samples, characterized by higher amounts of PD-1+, TIM-3+, LAG-3+ T cells compared to those who achieve a pCR^23. We therefore hypothesize that addition of PD-1 blockade on the backbone of dabrafenib and trametinib in the adjuvant setting for patient who do not achieve a pCR will improve RFS outcomes compared to historical controls. There have been a number of prior trials utilizing BRAF/MEK inhibition with anti PD-1/PD-L1 in melanoma (NCT02910700, NCT02130466, NCT02027961) including the COMBI-I study which utilized dabrafenib, trametinib and spartalizumab in metastatic melanoma patients with BRAF V600 mutations. This study demonstrated the safety and efficacy of this approach (see section 3.2.1 for further details) and thus we believe these agents will be appropriate for use in the adjuvant setting for the non pCR patients.

## 2.0 OBJECTIVES

### 2.1 PRIMARY OBJECTIVE

- To determine the 12-month relapse free survival (RFS) rate in stage IIIB/C/D melanoma patients who, after 8 weeks of neoadjuvant dabrafenib and trametinib, do not achieve a pCR and receive adjuvant dabrafenib, trametinib and spartalizumab

### 2.2 SECONDARY OBJECTIVES

- To evaluate the safety of neoadjuvant dabrafenib and trametinib and adjuvant dabrafenib, trametinib and spartalizumab
- To determine the 12-month relapse free survival (RFS) rate in stage IIIB/C/D
- Melanoma patients who, after 8 weeks of neoadjuvant dabrafenib and trametinib, achieve a pCR and receive adjuvant dabrafenib and trametinib.
- To assess the recurrence patterns, distant metastasis-free survival (DMFS), and overall survival (OS) in all patients treated on protocol.

### 2.3 EXPLORATORY OBJECTIVES

- To assess immunological and molecular features of treatment response and resistance
- To assess circulating markers and correlate them with treatment response and relapse and toxicity
- To assess the impact of neoadjuvant therapy on surgical resectability

### 3.0 STUDY DESIGN

[figure not shown]
This is an open-label single arm Phase II study that aims to examine the strategy of altering adjuvant therapy depending on pathologic response to neoadjuvant dabrafenib and trametinib therapy. Clinical stage III B/C/D BRAF V600E/K mutation with resectable disease will be enrolled. Patients will undergo 8 weeks of neoadjuvant dabrafenib and trametinib, followed by restaging scans and then definitive surgery if disease remains resectable. Surgical pathology will be analyzed for pathologic complete response (pCR), which is defined as absence of any residual tumor by H&E assessment.

Near pCR will be defined as less than 10% viable melanoma in the surgical specimen. Pathologic partial response (pPR) is defined as less than 50% viable tumor in the surgical specimen. No pathologic response (pNR) is defined as  $\geq 50\%$  viable tumor in the surgical specimen.

Patients who achieve a pCR will continue with adjuvant dabrafenib and trametinib for an additional 44 weeks in order to complete a total 1 year of therapy. Patients who do not achieve a pCR after 8 weeks of neoadjuvant dabrafenib and trametinib will receive dabrafenib, trametinib and spartalizumab in the adjuvant setting for a total of 44 weeks. Patients with no resectable disease after neoadjuvant therapy will be removed from the study and replaced.

Longitudinal blood and tumor will be collected in accordance with the study schedule.

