## 4.8 IMAGING ASSESSMENTS

Disease assessment will include imaging (computed tomography, magnetic resonance imaging) and physical examination (as indicated for palpable/superficial lesions). At screening, an MRI or CT of the head is required. At minimum, CT of the chest, abdomen and pelvis are required but additional imaging of affected areas (neck or extremities) may be required for documentation of target lesions.

Disease assessment will be completed within 35 days prior to the first dose of study drug, then as indicated in the Time and Events Tables Section 4.3. It is not necessary to repeat radiologic assessments at the final study visit if the subject was withdrawn due to disease progression. More frequent disease assessments may be performed at the discretion of the investigator. To ensure comparability between baseline and subsequent assessments, the same method of assessment and the same technique will be used when assessing response.

Disease response will be recorded as complete response (CR), partial response (PR), stable disease (SD), or progressive disease (PD) according to RECIST 1.1 criteria .

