## 7.0 DATA ANALYSIS AND STATISTICAL CONSIDERATIONS

### Overview

This will be a Phase II, open-label study of dabrafenib in patients with clinical Stage III melanoma who harbor a BRAF V600E or V600K mutation. In patients who achieve a pCR at the time of surgery, they will continue on dabrafenib and trametinib in the adjuvant setting. For those patients who do not achieve a pCR at the time of surgery, they will be treated with dabrafenib, trametinib and spartalizumab in the adjuvant setting.

The primary objective is to independently determine the 12-month relapse-free survival (RFS) rate in stage IIIB/C/D melanoma patients who, after 8 weeks of neoadjuvant dabrafenib and trametinib, do not achieve a pCR and receive adjuvant dabrafenib, trametinib and spartalizumab.

Secondary objectives include assessing safety in both the neoadjuvant and adjuvant settings. Recurrence patterns, including assessment of distant metastasis-free survival and overall survival separately by pathologic response status will also be addressed. The 12 month RFS of patients who achieve a pCR after receiving neoadjuvant and adjuvant treatment with dabrafenib and trametinib will also be assessed.

Exploratory objectives include assessing immune and molecular features of response and resistance, assessing the association between circulating blood markers and treatment response and relapse, and assessing surgical resectability.

A total of 45 patients will be initially treated with dabrafenib and trametinib for 8 weeks. Patients will be assessed for pCR as defined above based on the results of their surgical pathology. Patients who achieve a pCR will continue with the dabrafenib and trametinib combination for an additional 44 weeks. Patients who do not achieve a pCR will have spartalizumab added to dabrafenib and trametinib for an additional 44 weeks.

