### **Statistical Analyses**

For the primary objective, separately by group (patients who do/do not achieve a pCR at 8 weeks), the 12-month RFS rate will be estimated with a 95% confidence interval by using the Kaplan-Meier method. RFS is defined from time of surgery to any recurrence event (local or distant disease development or death due to melanoma. In addition, in patients who do not achieve a pCR, the 12-month RFS rate will be compared with the historical rate of 50% by using a two-sided exponential MLE test. Cox proportional hazards regression models will be fit to assess the association between various clinical, demographic, and disease covariates and RFS separately by pathologic response group.

For safety, the rate of grade 3+ adverse events will be tabulated and presented by group. For overall survival (OS) and distant metastasis-free survival (DMFS), 12-month rates will be reported with 95% confidence intervals, and Cox regression models will be used to assess the association between similar covariates as above and both OS and DMFS separately by group. OS is defined as time from treatment initiation to death. DMFS is defined as time from treatment initiation to development of documented distant metastatic disease outside the loco-regional site of the primary tumor or lymph node metastasis.

For the exploratory objectives, immunological and molecular features will be assessed quantitatively at baseline and at surgical resection. Kruskal-Wallis tests will be used to compare these parameters at each time point between responders (pCR) and non-responders (no pCR). Changes in each parameter from baseline to surgery will also be compared between responders and non-responders. Circulating tumor markers will be assessed at baseline and several on-study time points. Markers and changes in markers over time will be compared between responders and non-responders by using Kruskal-Wallis tests. In addition, generalized linear mixed models may be used to model these markers over time.

Finally, to assess the impact of neoadjuvant therapy on surgical resectability, a survey will be provided to surgeons regarding the difficulty of surgery (Appendix D). These data will be subjective and will be summarized graphically as numbers permit.

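### Treated patients who become unresectable are removed and replaced, yet OS and DMFS are to be reported in all treated patients, and nothing keeps the removed patients in follow-up to 12 months

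*Combined protocol and SAP*

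**What the plan says.** Section 3.0 (Study Design) gives the rule: "Patients with no resectable disease after neoadjuvant therapy will be removed from the study and replaced." The wording is removal from the study, not only from treatment. Under Section 4.9, patients who progress but stay resectable may still have surgery, and patients with an imaging complete response go on to lymph node dissection. The rule therefore reaches only those whose disease can no longer be resected.

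The secondary objective in Section 2.2 covers recurrence patterns, DMFS "and overall survival (OS) in all patients treated on protocol." Section 7.0 (Statistical Analyses) starts both endpoints before surgery: "OS is defined as time from treatment initiation to death", and "DMFS is defined as time from treatment initiation to development of documented distant metastatic disease". For these endpoints "12-month rates will be reported with 95% confidence intervals", with no population named.

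The Section 7.0 Overview describes the same objective by response group: "Recurrence patterns, including assessment of distant metastasis-free survival and overall survival separately by pathologic response status will also be addressed." Group membership needs a surgical specimen: "Patients will be assessed for pCR as defined above based on the results of their surgical pathology."

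**The concern.** These texts cannot all be carried out as written. The objective includes every treated patient from the first dose. The design rule takes some of them out and puts others in their place. The grouped analysis has no cell for a patient without a specimen. The overall 12-month rates can be read as covering everyone, but the plan does not say that removed patients are in them.

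The patients at issue are not a random subset. Becoming unresectable on neoadjuvant treatment is a treatment failure, so leaving these patients out would be expected to raise the reported OS and DMFS. An unstated analysis set also leaves the denominator to be settled after the data are known. The number who became unresectable bears directly on the exploratory objective about surgical resectability (Section 2.3), yet the plan does not require it to be reported.

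**Working it through.** **1. The plan's own figures.** The sample-size text needs 24 non-pCR patients: 24 / 0.60 = 40, raised to 45 for a higher pCR rate and dropout. The 40 reproduces. Unresectable patients are not mentioned there, and the plan gives no expected number of removals and no expected OS or DMFS rate. The sizes below therefore rest on assumptions.

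**2. How long a removed patient is observed.**
- Table 10 ends at Cycle 2 Day 28. Tables 11 and 12 schedule visits only after surgery, for pCR and non-pCR patients, to Week 52 and end of treatment.
- Adverse event recording and SAE capture run to 150 days after the last dose (Sections 5.0 and 5.3).
- Eight weeks of treatment is 56 days. 56 + 150 = day 206, or 206 / 30.44 = 6.8 months. The shortfall to 12 months is 365 − 206 = 159 days.
- Deaths up to day 206 could be captured as SAEs. Later metastases would not be collected systematically, because Section 5.1 excludes expected progression from the definition of an adverse event.
- Section 4.8 adds: "It is not necessary to repeat radiologic assessments at the final study visit if the subject was withdrawn due to disease progression."
- The 2 years of follow-up in the sample-size text is an assumption for RFS, not a follow-up instruction.

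**3. Overstatement if k removed patients are left out.** With 45 resected patients and k removed, let f = k / (45 + k). Then

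overstatement = f × (S_resected − S_removed).

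Assumed 12-month rates: S_resected 80–90%; S_removed 50–70% for OS and 0–50% for DMFS. The smallest and largest differences are 0.80 − 0.70 = 0.10 and 0.90 − 0.50 = 0.40 for OS, and 0.80 − 0.50 = 0.30 and 0.90 − 0 = 0.90 for DMFS.

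| k | f | OS overstated by (points) | DMFS overstated by (points) |
|---|---|---|---|
| 0 | 0 | 0 | 0 |
| 1 | 1/46 = 2.17% | 0.22–0.87 | 0.65–1.96 |
| 3 | 3/48 = 6.25% | 0.63–2.50 | 1.88–5.62 |

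The upper DMFS values need every removed patient to have distant metastasis by month 12 and to be left out of the analysis.

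**4. Scale against sampling error.** The 95% half-width is 1.96 × √(p(1 − p)/45): 11.7 points at p = 0.80, 10.4 at 0.85 and 8.8 at 0.90.

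**5. Whether censoring at removal repairs OS.** Take 45 resected patients with 6 deaths after surgery: the 12-month Kaplan-Meier estimate is 39/45 = 0.867. Add 3 patients censored at week 8, before any of those deaths. The risk set at each death is unchanged, so the estimate stays 0.867. Follow the 3 at an assumed 50–70% survival instead, and it becomes (39 + 1.5)/48 = 0.844 to (39 + 2.1)/48 = 0.856. Censoring at removal therefore gives the same OS estimate as leaving these patients out. A death during neoadjuvant treatment would alter the equality slightly.

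**The case against.** The strongest reply is that the effect is small and may be nil. Section 1.2 reports that all patients in the predecessor trial's initial report reached surgery on the same two drugs. A later count there gives 32 of 37 operated, with no reason stated for the other 5, so it settles nothing. OS and DMFS are secondary, are estimated with confidence intervals, and carry no decision rule. All of this stands, and it limits the weight of the point.

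A second reply is that Section 2.2 already names the population, so the natural reading puts removed patients in the denominator. That is a fair reading of the objective, but Section 3.0 says the opposite about their place in the study, and nothing says which text governs.

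Third, the loss is partial. Deaths to about day 206 are recordable, and a distant metastasis found at the Cycle 2 Day 28 restaging would already be on file. This is correct. What remains is later deaths, later metastases in patients unresectable for locoregional reasons, and the unstated analysis set. The imaging waiver in Section 4.8 concerns only the final visit and is weak support.

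Fourth, resected patients have no scheduled follow-up after end of treatment either, so one who stops early faces a similar gap. That also stands. Only the unresectable patients, however, are removed by an explicit rule.

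Finally, Figure 1 and the consent pages are not in the reviewed text. If either describes follow-up of removed patients, the gap narrows.

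**Conclusion.** The point holds. The removal rule in Section 3.0 conflicts with an objective set in all treated patients and timed from treatment initiation, and no available text follows the removed patients to 12 months. If the rule is applied, the bias is expected to run one way, towards better OS and DMFS, provided removed patients fare worse than resected ones.

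Its size is unknown. For one to three removals it is 0.2–2.5 points for OS and 0.7–5.6 for DMFS. These ranges assume the 12-month rates in the working and 45 resected patients. The plan gives 45 as total accrual, so the resected number could be lower and the fraction f slightly higher. The bias is smaller than the sampling error, but it is avoidable. The primary RFS analysis starts at surgery and is unaffected. This should be corrected, but it does not threaten the trial's main conclusion.

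**What to change.** In Section 3.0, replace the removal sentence with one saying that patients whose disease is unresectable after neoadjuvant therapy fall outside the resected RFS analysis set and may be replaced for that set, but stay in follow-up for survival and distant metastasis to at least 12 months from treatment start, subject to consent.

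In Section 7.0 (Statistical Analyses), state that 12-month OS and DMFS are reported once for all treated patients from treatment initiation, including these patients, and that the number who did not reach surgery is reported. The analyses by pathologic response group and the endpoint definitions stay as written.

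The cost is two sentences and status follow-up of what should be a few patients. DMFS counts documented distant disease, so routine-care records can supply it without added study imaging. The secondary rates may come out slightly less favourable. The figures of 24, 40 and 45 and the primary analysis do not change.
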